4.1.5. Cycle Length and Duration

Cycle 1 Day 1 is the day that the first dose of study drug is administered. Scheduled cycle length is 21 days. Actual Day 1 of subsequent cycles will correspond with the first day of administration of INCAGN01876 in that cycle; thus, treatment cycles may become out of sync with the originally planned schedule and cycle length may be different from 21 days. The date of the Day 1 of subsequent cycles recorded on the eCRF will be used as the Day 1 of the subsequent cycles.

4.2. Variable Definitions

The following variables will only be calculated if not reported on the eCRF.

4.2.1. Age

Subject age will be calculated as the integer part of the number of years from date of birth to the date of signing the ICF, using the following formula:

$$\text{Age} = \text{integer part of } (\text{date of informed consent} - \text{date of birth} + 1) / 365.25.$$

4.2.2. Prior and Concomitant Medication

Prior medication is defined as any nonstudy medication started before the first dose of INCAGN01876, pembrolizumab, or epacadostat.

Concomitant medication is defined as any nonstudy medication that is started accordingly:

- Before the date of first administration of INCAGN01876, pembrolizumab, or epacadostat and is ongoing throughout the study or ends on/after the date of first study drug administration.
- On/after the date of first administration of INCAGN01876, pembrolizumab, or epacadostat and is ongoing or ends during the course of study drug.

A prior medication could also be classified as "both prior and concomitant medication" if the end date is on or after first dose of INCAGN01876, pembrolizumab, or epacadostat. In the listing, it will be indicated whether a medication is prior-only, concomitant-only, or both prior and concomitant medication.

For the purposes of analysis, all medications will be considered concomitant medications unless the medications can unequivocally be defined as not concomitant.

5. STATISTICAL METHODOLOGY

5.1. General Methodology

Unless otherwise noted, SAS[®] software (SAS Institute Inc, Cary, NC; v9 or later) will be used for the generation of all tables, graphs, and statistical analyses. Descriptive summaries for continuous variables will include, but not be limited to, the number of observations, mean, standard deviation, median, minimum, and maximum. Descriptive summaries for categorical variables will include the number and percentage of subjects in each category.

5.2. Treatment Groups

This is an open-label, nonrandomized, Phase 1/2 study to determine the safety, tolerability, and efficacy of INCAGN01876 when given in combination with immune therapies.

In Phase 1 (Dose Escalation), a higher starting dose of INCAGN01876 [REDACTED] was used based on safety data from the monotherapy study (INCAGN 1876-101) in Treatment Group A, but it did not exceed 1 dose level below the highest tolerated dose of INCAGN01876 monotherapy. The higher dose was communicated to investigational sites with an administrative letter. Phase 1 Treatment Group A serves as a safety run-in phase for Phase 2 Treatment Group C.

In Phase 2 (Dose Expansion), melanoma, RCC, and UC subjects will be enrolled into Treatment Group C [REDACTED].

[REDACTED]

[REDACTED]

5.3. Analysis Populations

5.3.1. Full Analysis Set

The FAS includes all subjects enrolled in the study who received at least 1 dose of INCAGN01876, pembrolizumab, or epacadostat.

Specific FAS populations to be used for drug-specific tables include the following subgroups:

- INCAGN01876 FAS population.
- Pembrolizumab FAS population.
- Epacadostat FAS population.

5.3.2. Response Evaluable Populations

The response evaluable population includes all subjects enrolled in the study who have received at least 1 dose of INCAGN01876, pembrolizumab, or epacadostat; completed a baseline scan; and met at least 1 of the following criteria:

- The subject has ≥ 1 postbaseline scan OR
- The subject has been on the study for a minimum of 70 days of follow-up OR
- The subject has discontinued from treatment.

6. BASELINE, EXPOSURE, AND DISPOSITION VARIABLES AND ANALYSES

[Appendix A](#) provides a list of data displays. Sample data displays will be provided in a separate document.

6.1. Baseline and Demographics, Physical Characteristics, and Disease History

6.1.1. Demographics

The following demographics will be summarized for the FAS population [REDACTED]: age, sex, race, ethnicity, weight, and height.

6.1.2. Baseline Disease Characteristics and Disease History

Disease histology, stage at initial diagnosis, current stage, and primary site of disease will be summarized for all subjects in the FAS population [REDACTED]. ECOG performance status will also be summarized for all subjects in the FAS population [REDACTED].

6.1.3. Prior Therapy

Number of prior systemic cancer therapy regimens will be summarized for all subjects in the FAS population [REDACTED]. Regimen name, component drugs, start and stop date, route of the medication, purpose of the regimen, best response, reason for discontinuation, and date of relapse/progression will be listed.

Number of subjects who received prior radiation and number of subjects who had prior surgery or surgical procedure for the malignancies under study will be listed.

6.1.4. Medical History

Medical history recorded on the eCRF will be presented in the subject data listings.

6.2. Disposition of Subjects

The number and percentage of subjects who were enrolled, treated, discontinued study treatment with a primary reason for discontinuation, and withdrawn from the study with a primary reason for withdrawal will be summarized for the FAS population [REDACTED].

6.3. Protocol Deviations

Protocol deviations recorded on the eCRF will be presented in the subject data listings.

6.4. Exposure

6.4.1. Exposure for INCAGN01876

For subjects in the FAS population, exposure to INCAGN01876 will be summarized descriptively as the following:

- **Total number of infusions:** Total number of infusions per subject with a nonzero dose of INCAGN01876.

6.4.2. Exposure for Pembrolizumab

The exposure for pembrolizumab will be summarized the same as that for INCAGN01876 in Section 6.4.1.

6.4.3. Exposure for Epacadostat

For subjects in the FAS population, exposure to epacadostat will be summarized descriptively as the following:

- **Duration of treatment (days):** Date of last dose of epacadostat – date of first dose of epacadostat + 1.

6.5. Prior and Concomitant Medication

For subjects in the FAS population, prior medications and concomitant medications will be coded using the WHO Drug Dictionary and summarized by WHO drug class and WHO drug term for the FAS population [REDACTED]

[REDACTED]. Results will be summarized as number and percentage of subjects with prior and concomitant medications by PT and WHO drug class.

7. EFFICACY

Appendix A provides a list of data displays. Sample data displays will be provided in a separate document.

7.1. General Considerations

Due to the early discontinuation of study enrollment, only ORR using RECIST v1.1 will be summarized for the FAS population [REDACTED].

7.2. Analysis of the Objective Response Rate

7.2.1. Objective Response Rate and Best Overall Response by RECIST v1.1

Best overall response is defined as the best response recorded postbaseline prior to and including the first PD, in the order of CR, PR, SD, PD, and NE. In the case of SD, measurements must meet the SD criteria at least once after the date of first dose of study treatment at a minimum interval of 56 (63 – 7) days. Subjects who fail to meet this criterion will have a best overall response of PD if the next available assessment indicates PD or NE if there is no additional assessment available.

Objective response rate, defined as the proportion of subjects with overall responses, will be summarized for all subjects in the FAS population [REDACTED].

For subjects with measurable disease at baseline, the RECIST v1.1 assessment criteria presented in Table 7 can be used to determine the overall disease status at a given timepoint based on the target lesion, nontarget lesion, and new lesion assessment.

Table 7: RECIST v1.1 Evaluation Criteria for Overall Response: Measurable Disease at Baseline

Target Lesions	Nontarget Lesions	New Lesions	Overall Response
CR	CR	No	CR
CR	Non-CR/non-PD	No	PR
CR	NE	No	PR
PR	Non-PD or NE	No	PR
SD	Non-PD or NE	No	SD
Not all evaluated	Non-PD	No	NE
PD	Any	Yes or No	PD
Any	PD	Yes or No	PD
Any	Any	Yes	PD

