2.2. Study Endpoints

2.2.1. Primary Endpoints

- Safety and tolerability will be assessed by monitoring frequency, duration, and severity of AEs.
- ORR, defined as the percentage of subjects having CR or PR, will be determined by investigator assessment of radiographic disease assessments per RECIST v1.1.
- CRR, defined as the percentage of CPI-naive melanoma subjects who have a CR as determined by investigator assessment of radiographic disease assessments per RECIST v1.1.

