7.7.2.2. Response Evaluation Criteria in Solid Tumors Version 1.1 Tumor Imaging During Treatment

The first imaging assessment should be performed 9 weeks after the first dose of INCAGN01876 and then every 9 weeks (± 7 days) for the first 12 months and then every 12 weeks (± 7 days) thereafter until disease progression is determined. Imaging assessments may be done more frequently if clinically indicated. **Imaging should follow calendar days and should NOT be delayed for delays in cycle starts.**

Per mRECIST, response should be confirmed by a repeat radiographic assessment not less than 4 weeks from the date the response was first documented. The scan for confirmation of response may be performed at the earliest 4 weeks after the first indication of response or at the next scheduled scan, whichever is clinically indicated.

Imaging should continue to be performed until documented disease progression, the start of new anticancer treatment, withdrawal of consent, death, or the end of the study, whichever occurs first. Disease progression should be confirmed at least 4 weeks, but no more than 6 weeks, later after the first scan indicating disease progression in clinically stable subjects. Subjects who have unconfirmed disease progression may continue on treatment until progression is confirmed, provided that they have met the conditions detailed in [Section 7.7.1](#). A central imaging vendor will not be used in this study.

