10.1.2. Efficacy Analyses

Only ORR will be summarized per RECIST v1.1. The analyses for other efficacy endpoints and analyses per mRECIST will be eliminated.

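### The SAP's single efficacy result is an unconfirmed, investigator-read ORR; label it as such and report the confirmed count beside it

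*SAP*

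**What the plan says.** - SAP 7.2.1, best response: "Best overall response is defined as the best response recorded postbaseline prior to and including the first PD".
- SAP 7.2.1, stable disease: "In the case of SD, measurements must meet the SD criteria at least once after the date of first dose of study treatment". The required gap is 56 days or more. No interval or repeat scan is set for CR or PR.
- SAP 7.2.1, ORR: "Objective response rate, defined as the proportion of subjects with overall responses". Confirmation is not mentioned.
- Protocol 2.2.1, primary endpoint: "ORR, defined as the percentage of subjects having CR or PR, will be determined by investigator assessment of radiographic disease assessments per RECIST v1.1". Confirmation is not mentioned here either.
- Protocol 7.7.2.2, the only rule on confirming a response: "Per mRECIST, response should be confirmed by a repeat radiographic assessment not less than 4 weeks from the date the response was first documented". The confirming scan may be done from 4 weeks onward or at the next scheduled assessment. The same section says that there is no central imaging vendor.
- SAP 7.1, because enrollment stopped early: "only ORR using RECIST v1.1 will be summarized for the FAS population".
- SAP 10.1.2: "The analyses for other efficacy endpoints and analyses per mRECIST will be eliminated".
- SAP Appendix A lists three efficacy displays: Table 2.1.1 (ORR under RECIST v1.1), Listing 2.6.1 (best overall response) and Listing 2.6.2 (ECOG status).

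**The concern.** The weaker category has a persistence rule and the category that drives the result has none. An early stable-disease reading followed by progression is downgraded, while one PR reading followed by progression counts as a response.

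Duration of response, which would have shown whether responses lasted, goes with the other endpoints. So does the mRECIST ORR, the only analysis linked to a confirming scan. What remains is one rate, read by unblinded sites in a single-arm setting. A reader of the synoptic report could not tell from Table 2.1.1 whether it counts confirmed or unconfirmed responses. With few subjects enrolled, one responder can move the rate by several points.

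**Working it through.** The documents give no figure for the effect of omitting confirmation, so there is none to reproduce. The check applies the rules to example scan sequences, followed by simple arithmetic.

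**1. What the SAP rule does.** The sequences are illustrative; scheduled scans fall at weeks 9 and 18.

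| Readings | Best response, SAP 7.2.1 | Counted in ORR | Confirmed at 4 weeks or more |
|---|---|---|---|
| PR week 9, PR week 18 | PR | yes | yes |
| PR week 9, PD week 18 | PR | yes | no |
| PR week 9, no later scan | PR | yes | cannot be judged |
| SD at an unscheduled week 6 scan (day 42, below 56), PD week 9 | PD | no | not applicable |

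Rows 2 and 3 are where the two rates can differ.

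**2. Direction.** Let U be the responders counted under SAP 7.2.1 and C those whose CR or PR persists on a repeat scan at least 4 weeks later, both from the same RECIST v1.1 readings and over the same n. Every confirmed responder is also a counted responder, so C ≤ U and

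U/n − C/n = (U − C)/n ≥ 0.

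The two rates are equal only when every counted response is confirmed.

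**3. Size.** The share of responses that would fail confirmation is not in the documents, and SAP 10.1.1.2 says only that a limited number entered Treatment Group C. Per unconfirmed responder the difference is 1/n (n assumed):

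- n=6: 1/6 = 16.7 points
- n=10: 1/10 = 10 points
- n=20: 1/20 = 5 points

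**4. Can the confirmed count come from the planned schedule?** Scans are 9 weeks (63 days) apart with a window of ±7 days each, so two consecutive scheduled scans are at least 63 − 14 = 49 days apart, more than the 28 days needed. After 12 months the gap is 12 weeks. The next scheduled scan can therefore serve as the confirming scan.

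**5. Why a third row is needed.** Write U = C + N + F, where N is responders with no later scan and F those whose response was not maintained. With invented counts n=20, U=8, C=6, N=1, F=1, the unconfirmed ORR is 8/20 = 40%, the confirmed ORR is 6/20 = 30%, and N/n is 1/20 = 5%. Reporting C alone would treat N as failures without saying so.

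**The case against.** The strongest reply is that the SAP follows the protocol. Primary ORR in Protocol 2.2.1 and 9.4.1.1, and in SAP 2.3.1, is CR or PR by investigator under RECIST v1.1, with no confirmation step. A reader might infer that the SAP stripped confirmation from the primary endpoint. It did not. The dropped mRECIST ORR was secondary and was never named a confirmed ORR, and its removal is openly listed and explained by the end of enrollment. This stands, and it is why the protocol-defined rate should be kept.

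Further points for the other side:

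- **Confirming scans are not guaranteed.** Protocol 7.7.2.2 is permissive about timing, and the extra scan at 4 to 6 weeks in the schedule of assessments is for progression only. After early closure some responders may have no second scan. This stands; the fix gives them their own row.
- **Dropping mRECIST does not act in one direction only.** Protocol 1.5.4.1.1 and 7.7.1 allow for response after an initial, unconfirmed progression, whereas SAP 7.2.1 stops at first PD and excludes such responses. A reader might infer that removing mRECIST must raise the reported rate; the documents do not support that. The inequality above holds only within the same RECIST v1.1 readings.
- **The historical rates may be unconfirmed too.** Protocol 1.5.1 gives ongoing response durations from 1+ day in both RCC and UC, which suggests that some responses had no 4-week scan at cutoff. This is an inference, but it favours showing both counts, with the unconfirmed one for like-for-like comparison.
- **Precision is poor anyway.** At an assumed 8/20 the exact 95% interval is about 19% to 64%, far wider than a 5-point shift. That limits the importance of the point. It does not remove the need to say what is being counted.

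**Conclusion.** The point holds as a minor one about reporting. The only efficacy result is an unconfirmed, investigator-read ORR that is not labelled as such, and it can only equal or exceed the confirmed rate on the same readings and denominator. The size of the difference is unknown. The 1/n figures rest on assumed values of n.

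Two stronger readings are not supported:

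- A reader might infer that the reported ORR is biased upward. That would require at least one counted response to fail confirmation, and it holds only relative to a confirmed rate that the protocol never made its primary endpoint.
- A reader might infer that the error rates of the Simon designs are compromised. SAP 9 and 10.1.4 cancel the interim, Simon and Bayesian analyses. The ORR is therefore descriptive, and no decision rule is applied to it.

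**What to change.** - **SAP 7.2.1:** state that ORR follows the protocol definition and does not require confirmation. Define confirmed response as CR or PR that persists on a repeat scan at least 4 weeks later.
- **Table 2.1.1:** keep the protocol-defined ORR, labelled unconfirmed and investigator-read. Add a row for confirmed ORR and a row for responders with no later scan. Use one denominator for all rows. The legible text of SAP 7.1 and 7.2.1 names the FAS while Appendix A gives the response evaluable population for this table. Text after the FAS is redacted, so the sponsor should check that the two agree.
- **Listing 2.6.1:** flag each responder as confirmed, not confirmed, or without a later scan. The listing shells are in a separate document, so this may already be partly covered.

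The cost is a few lines of SAP text and a little extra programming, with no new scans. The downside is that the confirmed figure may be lower than the headline ORR, partly because early closure leaves some responders without a second scan. The third row makes that part visible.

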4.5. Overall Study Duration

The study begins when the first subject signs the ICF. The end of the study will occur when all subjects have discontinued treatment, and the last follow-up visit has been performed.

If there are ≤ 5 subjects on study for more than 6 months, a database lock of the study may occur to allow for the analysis of the study data. Any remaining subjects may continue to receive study treatment and be seen by the investigator per usual standard of care for this population. The investigator will be expected to monitor for and report any AEs, SAEs, pregnancies, and deaths as detailed in [Section 8](#) and [Section 6.4.3](#). The remaining subjects are considered to be on study until a discontinuation criterion is met and written notification is provided to the sponsor.

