9. STATISTICS

9.1. Study Populations

The full analysis set includes all subjects enrolled in the study who received at least 1 dose of study treatment (INCAGN01876, pembrolizumab, or epacadostat). This population will be used in the analyses of demographic, baseline, safety, study treatment administration, and efficacy data.

[REDACTED]

[REDACTED]

The biopsy evaluable population includes subjects who received at least 1 dose of study treatment (INCAGN01876, pembrolizumab, or epacadostat) and had at least 1 biopsy sample collected and analyzed. During Phase 2 of the study, biopsy cohorts will be added for each treatment group (C and D). A subject who does not meet the biopsy requirements for the study will be replaced within the biopsy cohort.

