APPENDIX A. PLANNED TABLES AND FIGURES

Due to the early termination of study enrollment, a synoptic CSR will be provided. This appendix provides a list of the planned tables and listings for the synoptic CSR. Standard tables will follow the conventions in the Standard Safety Tables initial version. Shells are provided for nonstandard tables. In-text tables are not needed for the synoptic CSR.

The list of tables and listings and the shells are to be used as guidelines. Modifications of the list or shells that do not otherwise affect the nature of the analysis will not warrant an amendment to the SAP.

Tables

Table No.	Title	Population	Standard
Baseline and Demographic Characteristics			

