1.4 Prior Medication and Concomitant Medication			
1.4.1	Summary of Prior Cancer Therapy	FAS	
1.4.2	Summary of Prior Medications	FAS	X
1.4.3	Summary of Concomitant Medications	FAS	X
Efficacy			
2.1.1	Summary of Objective Response Rate Under RECIST v1.1	Response Evaluable	
Safety			

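### The SAP text puts ORR on the full analysis set, but its only efficacy table is specified on the response-evaluable population, and no change of population is recorded.

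*SAP*

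**What the plan says.** Three places assign ORR, or efficacy generally, to the full analysis set (FAS):

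- SAP 7.1: "only ORR using RECIST v1.1 will be summarized for the FAS population".
- SAP 7.2.1: "Objective response rate, defined as the proportion of subjects with overall responses, will be summarized for all subjects in the FAS population".
- Protocol 9.1, of the full analysis set: "This population will be used in the analyses of demographic, baseline, safety, study treatment administration, and efficacy data".

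One place does not. In SAP Appendix A, the only table under Efficacy is Table 2.1.1, "Summary of Objective Response Rate Under RECIST v1.1", and its population is given as Response Evaluable. No FAS version is listed.

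SAP 10.1.2 records what changed in the efficacy analyses: "Only ORR will be summarized per RECIST v1.1. The analyses for other efficacy endpoints and analyses per mRECIST will be eliminated". It says nothing about the population.

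**The concern.** ORR is a Phase 2 primary endpoint and, after enrollment stopped early, the only efficacy result the SAP keeps. A programmer cannot follow both Section 7 and Appendix A: one gives a rate over all treated subjects, the other a rate over a subset. If the subset was intended, it is an unrecorded departure from the visible text of Protocol 9.1. If it was not intended, the table specification is wrong. Either way, the denominator of the one efficacy figure is open to choice after the data are seen, and the two choices can differ in only one direction.

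**Working it through.** There is no plan figure to reproduce. The check compares definitions and then works out what a difference would do.

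**1. The two sets.**

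| | FAS (SAP 5.3.1) | Response evaluable (SAP 5.3.2) |
|---|---|---|
| At least 1 dose of any study drug | required | required |
| Completed baseline scan | not required | required |
| One of: a postbaseline scan, at least 70 days of follow-up, treatment discontinued | not required | required |

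The response-evaluable set is thus a subset of the FAS.

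**2. Who drops out.** There are two routes:

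- a treated subject with no baseline scan;
- a subject still on treatment with no postbaseline scan and under 70 days of follow-up. This can arise only at an early data cut.

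A subject who stops treatment before any postbaseline scan stays in, provided there was a baseline scan.

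**3. Direction.** A RECIST v1.1 response needs both a baseline and a postbaseline assessment. Every dropped subject lacks one of them, so none can be a responder. The numerator x is the same in both sets.

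**4. Size.** With N treated, k dropped and x responders:

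- FAS ORR = x/N
- Table 2.1.1 ORR = x/(N−k)
- Ratio = N/(N−k)

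| N | k | Ratio | Example |
|---|---|---|---|
| any | 0 | 1.00 | no change |
| 6 | 1 | 6/5 = 1.20 | 1/6 = 16.7% becomes 1/5 = 20.0% (+3.3 points) |
| 10 | 1 | 10/9 = 1.11 | 3/10 = 30.0% becomes 3/9 = 33.3% (+3.3 points) |
| 20 | 1 | 20/19 = 1.05 | 6/20 = 30.0% becomes 6/19 = 31.6% (+1.6 points) |

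N = 6 is the minimum number of evaluable subjects that SAP 10.1.1.1 reports for Treatment Group A. It is not a stated FAS size. The other N, and every k and x, are assumptions, because the documents do not give them.

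**5. Is Table 2.1.1 the odd one out?** Yes. The Appendix A populations for demographics, disposition, medications, the overall adverse event tables and laboratory shifts match the body text. The exposure and drug-related adverse event tables use drug-specific FAS subsets, which SAP 5.3.1 provides for. Nothing visible in the SAP assigns the response-evaluable set to any analysis except that one table cell.

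**The case against.** The strongest reply is that the two denominators should coincide in practice.

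- **Follow-up route.** The SAP covers final analyses only (Section 1) and has no interim analyses (Section 9). Protocol 4.5 says: "The end of the study will occur when all subjects have discontinued treatment, and the last follow-up visit has been performed". Discontinuation alone satisfies an evaluability criterion. That section also allows an earlier lock once 5 or fewer subjects have been on study for more than 6 months; on the natural reading those subjects are past 70 days as well.
- **Baseline-scan route.** Protocol 7.7.2.1 makes baseline imaging mandatory, and measurable disease is an inclusion criterion. A treated subject without a baseline scan would be a protocol violation.

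This stands: k may be zero. It limits the size of the effect but does not reconcile the text.

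Other points carry part of their weight:

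- **Visibility.** Table 1.1.1 and Listings 2.3.1 and 2.6.1 would let a reader recompute ORR on either set. That lowers the risk of a hidden difference; it does not say which rate is the planned one.
- **Evaluable subjects in the protocol.** Protocol 9.2.3 and 9.6.1 count responses among evaluable subjects for the Simon designs, so such a denominator is not foreign to the protocol. Those analyses will not be performed (SAP 10.1.4), and Protocol 9.1 still names the full analysis set for efficacy.
- **Redactions.** Text is blacked out after the FAS reference in SAP 7.1 and 7.2.1, and within Protocol 9.1. A further population cannot be excluded. But the same blacked-out pattern follows the FAS in the SAP's demographic, disposition and adverse event sections, and even a second population would leave the promised FAS summary without a table.
- **Status of Appendix A.** It describes its lists as guidelines and adds: "Modifications of the list or shells that do not otherwise affect the nature of the analysis will not warrant an amendment to the SAP". Whether a change of ORR denominator fits that waiver is unclear, and the clause does not say whether Section 7 or the table list governs.
- **SAP 10.1.2.** Its silence is an omission only if the response-evaluable set was intended. That is right, and it is why the fix has two branches.

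**Conclusion.** The inconsistency is real and visible in the text: the FAS in SAP 7.1, SAP 7.2.1 and Protocol 9.1, the response-evaluable set in the only efficacy table, and no recorded change. Any numerical difference makes the table's ORR higher, by the factor N/(N−k). That is nil at k = 0 and, for one dropped subject, between 1.05 and 1.20 over the assumed range N = 20 down to N = 6. At the final analysis it is likely to be small or nil. No go/no-go decision depends on it, because the Simon and Bayesian analyses have been dropped. It should still be corrected before the output is produced, since a sole efficacy result needs one denominator named in advance. Confidence is high on the mismatch; whether ORR would actually change cannot be determined from the documents.

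**What to change.** Preferred: in SAP Appendix A, change the population of Table 2.1.1 to FAS, and state that treated subjects without an evaluable response count as non-responders. SAP 7.2.1 already implies this by keeping all FAS subjects and allowing a best response of not evaluable, so the statement only makes it explicit. A response-evaluable rate may be added as a labelled supportive column. Cost: one cell and, optionally, one column.

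If the response-evaluable set was intended: amend the sentences in SAP 7.1 and 7.2.1 and add a line to SAP 10.1.2 recording the departure from Protocol 9.1. Cost: two sentences and one line. Neither route needs new data.
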